5.1.2 Autologous Bone Marrow Harvest Period (Visit 2)

The source of CD34+ HSCs will be BM. The harvesting of autologous bone marrow will be performed for subjects who meet the inclusion and exclusion criteria at Visit 1. Two assessments will be performed during the hospital admission for BM harvest. This planned hospitalization for protocol procedures will not constitute a SAE.

Pre-harvest procedure (Assessment A)

Once a date for harvest has been scheduled, the pre-harvest procedure will commence up to 5 days beforehand. The results of these pre-operative tests must meet the requirements that permit the harvest of autologous BM, according to standard guidelines in the institution. Pre-harvest tests include:

- Medical history since screening (including AEs and concomitant medications) and physical examination,
- Weight (this measurement will be used for OTL-101 product dose calculation),
- Hematology (see [Table 3](#)),
- Prothrombin or INR and PTT,

- Biochemistry; including magnesium and phosphate (see [Table 3](#)),
- Type and cross-matching for one unit of packed RBC (PRBC) (to be performed within the period required by the blood bank),
- Serum HCG (pregnancy test) if female of child-bearing age (and if more than 28 days have elapsed since the screening test),
- Urinalysis.

Bone Marrow Harvest (Assessment B)

For BM harvesting, a central venous access device will be required (if not already in place) for ease of phlebotomy and drug administration. The decision between PICC line, a tunneled central venous catheter, or an implanted subcutaneous access device will be made by discussions with subjects parents and line placement surgeon. A PICC line or central venous line may instead be placed as a separate procedure with appropriate sedation or during the general anesthesia for the BM harvest.

The harvest procedure will involve a bilateral BM aspiration in the posterior iliac crests, where a total volume required should be between 15-20 ml/kg of the subjects body weight. The BM sample will be directly transported to the GMP manufacturing location.

Compatible irradiated PRBC (10 to 15 cc/kg) may be transfused following the completion of marrow harvest, if considered appropriate by the Investigator.

If the subject is otherwise well, he/she may be discharged to home, 1-2 days after harvest.

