5.1.3 Baseline (Visit 3)

Pre-Conditioning (Assessment C)

After BM harvest and if the autologous OTL-101 product has met the release criteria ([Section 3.7.1](#)), additional baseline samples must be collected for the following tests within 1 week before the first administration of Busulfan:

- Physical examination, including vital signs (temperature, pulse rate, respiratory rate and blood pressure). Temperature can be measured as per standard clinic practice,

- Hematology (see [Table 3](#)),
- Prothrombin or INR and PTT,
- Biochemistry (see [Table 3](#)),
- Serum HCG (pregnancy test) if female of child-bearing age (and if more than 28 days have elapsed since the screening test),
- Urinalysis,
- Pulse oximetry,
- Interval history (including routine review of systems, including infectious symptoms (e.g., fever), AEs and concomitant medications),
- Measurement of immune function:
 - Absolute numbers of CD3+, CD4+ and CD8+ T-lymphocytes, CD19+ B-lymphocytes and CD56+/CD16+ (or CD56+/CD3-) NK cells, CD4+/CD45RA+ (naïve) and CD4+/CD45RO+ (memory) T cells,
 - TREC levels,
 - TCR V β usage,
 - lymphocyte response to phytohemagglutinin (PHA) (if sufficient cells),
 - Serum immunoglobulin (IgG, IgA, IgM).

Please note: the above immune function tests can be performed at any point after provision of consent/assent and prior to Busulfan administration in younger subjects if deemed appropriate by the Investigator.

- Peripheral blood mononuclear cells (PBMC) and serum banking for RCL determination. These tests can be performed at any time following BM harvest (Visit 2: Assessment B) and prior to OTL-101 administration (Visit 3: Assessment F) in younger subjects if deemed appropriate by the Investigator.
- Measurements of erythrocyte ADA enzymatic activity and erythrocyte deoxyadenine nucleotide levels. These tests can be performed at any time following BM harvest (Visit 2: Assessment B) and prior to OTL-101 administration (Visit 3: Assessment F) in younger subjects if deemed appropriate by the Investigator.

The Investigator must ensure a PICC line or central venous catheter is in place prior to the start of Busulfan conditioning.

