| Study Period | Screening | Pre-harvest Assessment | Bone Marrow Harvest | Baseline | Conditioning | | OTL-101 Treatment | Short-term Follow-up | | | | | | | |
|-------------------------------------|----------------------------|--------------------------------|---------------------------------|----------------|----------------|--------------|-------------------|----------------------|-------|-------|--------|--------|--------|--------|---|
| | | | | | 3 ¹ | 3 | | 3 | 3 | 3 | 3 | 3 | 3 | 3 | 3 |
| Visit number | 1 | 2 ¹ | 2 | 3 ¹ | 3 | 3 | 3 | 3 | 3 | 3 | 3 | 3 | 3 | 3 | 3 |
| Assessment number | | A | B | C | D | E | F | G | H | I | J | K | L | M | |
| Visit window | | | | | | | | +/-2 days | | | | | | | |
| Day | Within 60 days of Visit 2B | Up to 5 days prior to Visit 2B | Approx 30 day prior to Visit 3F | Day-10 to -4 | Day -4 to -3 | Day -2 to -1 | Day 0 | Day 1 | Day 4 | Day 8 | Day 11 | Day 15 | Day 19 | Day 24 | |
| Informed Consent/Assent | X | | | | | | | | | | | | | | |
| Eligibility check | X | | | | | | | | | | | | | | |
| Demographic Data | X | | | | | | | | | | | | | | |
| Medical History | X | X | | | | | | | | | | | | | |
| Physical examination | X | X | | | X | | | | | | | | | | |
| Vital Signs | X | | | | X | | | X ² | | | | | | | |
| Weight (kg) | X | X | | | | X | | | | | | | | | |
| Height (cm) | X | | | | | | | | | | | | | | |
| Biochemistry sample ³ | X | X | | | X | | | X | X | X | X | X | X | X | |
| Hematology sample ⁴ | X | X | | | X | | | X | X | X | X | X | X | X | |
| PT or PTT/INR | X | X | | | X | | | | | | | | | | |
| PB or BM cytogenetics ⁵ | X | | | | | | | | | | | | | | |
| HIV-1/Hep B/Parvo B19 | X | | | | | | | | | | | | | | |
| Serum pregnancy test ⁶ | X | X | | | X | | | X | | | | | | | |
| Urinalysis ⁷ | X | X | | | X | | | | | | | | | | |
| ECG | X | | | | | | | | | | | | | | |
| Echocardiogram | X | | | | | | | | | | | | | | |
| Chest X-ray ⁸ | X | | | | | | | | | | | | | | |
| Pulse oxymetry | X | | | | X | | | | | | | | | | |
| Biopsy of skin lesions | X | | | | | | | | | | | | | | |
| ADA-SCID diagnosis confirmation | X | | | | | | | | | | | | | | |
| Questionnaire/QoL scale | X | | | | | | | | | | | | | | |
| Infectious episodes | X | | | | X | | | | | | | | | | |
| Adverse events | | X | X | X | X | X | X | X | X | X | X | X | X | X | |
| Concomitant Medication ⁹ | | X | X | X | X | X | X | X | X | X | X | X | X | X | |
| Type and cross PRBC | | X | | | | | | | | | | | | | |

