| Bone marrow harvest | | | X | | | | | | | | | | | | |

| Study Period | Screening | Pre-harvest Assessment | Bone Marrow Harvest | Baseline | Conditioning | | OTL-101 Treatment | Short-term Follow-up | | | | | | |
|--|----------------------------|--------------------------------|---------------------------------|-----------------|-----------------|-----------------|-------------------|----------------------|-------|-------|--------|--------|--------|--------|
| | | | | | 3 ¹ | 3 | | 3 | 3 | 3 | 3 | 3 | 3 | 3 |
| Visit number | 1 | 2 ¹ | 2 | 3 ¹ | 3 | 3 | 3 | 3 | 3 | 3 | 3 | 3 | 3 | 3 |
| Assessment number | | A | B | C | D | E | F | G | H | I | J | K | L | M |
| Visit window | | | | | | | | +/-2 days | | | | | | |
| Day | Within 60 days of Visit 2B | Up to 5 days prior to Visit 2B | Approx 30 day prior to Visit 3F | Day-10 to -4 | Day -4 to -3 | Day -2 to -1 | Day 0 | Day 1 | Day 4 | Day 8 | Day 11 | Day 15 | Day 19 | Day 24 |
| PRBC transfusion | | | X | | | | | | | | | | | |
| Immune function ¹⁰ | | | | X ¹¹ | | | | | | | | | | |
| PBMC banking for RCL | | | | X ¹² | | | | | | | | | | |
| Serum banking for RCL | | | | X ¹² | | | | | | | | | | |
| Erythrocyte ADA enzymatic activity | | | | X ¹² | | | | | | | | | | |
| Erythrocyte deoxyadenine nucleotide levels | | | | X ¹² | | | | | | | | | | |
| Busulfan administration | | | | | X | X | | | | | | | | |
| PK samples | | | | | X ¹³ | X ¹⁴ | | | | | | | | |
| OTL-101 administration | | | | | | | X | | | | | | | |

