| 1. Subjects will be admitted to the hospital for Visits 2 and 3. 2. During the infusion of OTL-101 vital signs will be monitored according to standard institute protocols. 3. Biochemistry samples will include the assessment of parameters listed in Table 3. Albumin ALT, AST, ALP will be measured at all time points indicated in this table. Total bilirubin, total protein, creatinine, blood urea, sodium, potassium, chloride, and calcium will be measured at screening, baseline, Day 1 and all follow-up visits (Month 1 to Month 24). Magnesium and phosphate will be measured only at pre-harvest and baseline time points. 4. Hematology samples will include the assessment of parameters listed in Table 3 and will be measured at all time points indicated in this table. 5. If cytogenetic testing was not performed on cells from amniocentesis, assessment should be by karyotype, CGH, and WES 6. Serum pregnancy tests are required in females of child-bearing potential at screening, prior to bone marrow harvest, prior to conditioning (Busulfan) treatment, and before the infusion of OTL-101. Any positive test will immediately result in the withdrawal of the subject from the study and should be reported as per guidance in Section Error! Reference source not found. 7. Urinalysis will include the assessment of parameters listed in Table 3 and will be measured at all time points indicated in this table. Any abnormalities detected on dipstick at Screening, Pre-harvest and Baseline will require repeat dipstick and microscopic examinations. 8. If there is any evidence of severe lung disease on the screening chest X-ray, a CT scan is required in order to establish if the subject meets any of the specified pulmonary exclusion criteria defined in Section Error! Reference source not found. 9. Standard post-transplant medication will be administered from Day 0 and recorded in the eCRF. 10. Immune function will be assessed absolute numbers of CD3+, CD4+ and CD8+ T-lymphocytes, CD19+ B-lymphocytes and CD56+/CD16+ (or CD56+/CD3-) NK cells, CD4+/CD45RA+ (naïve) and CD4+/CD45RO+ (memory) T cells, TREC levels, TCR Vβ usage, lymphocyte response to PHA (if sufficient cells), and serum immunoglobulin (IgG, IgA, IgM). 11. The immune function tests required for Visit 3, Assessment C can be performed at any point after provision of consent/assent and prior to Busulfan administration in younger subjects if deemed appropriate by the Investigator. 12. These test can be performed at anytime following BM harvest (Visit 2: Assessment B) and prior to OTL-101 administration (Visit 3: Assessment F) in younger subjects if deemed appropriate by the Investigator. | | | | | | | | | | | | | | |

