8.3 Efficacy Evaluations

8.3.1 Primary Efficacy Endpoints

8.3.1.1 Response to OTL-101 Treatment at 6 Months

Response to OTL-101 treatment at 6 months post administration will be based on the following criteria:

- ADA activity in red blood cells: change from baseline >0 Units,
- Absolute CD3+ T-cell count $\geq 200/\text{mm}^3$, and
- Detectable gene-marked granulocytes by differential polymerase chain reaction (dPCR)/qPCR $\geq 1/10,000$ cells.

Subjects who meet all three criteria will be said to have mounted a response.

For any subjects with missing values at 6 months, the earliest assessments after month 6 will be used. In addition, if ADA activity at baseline is not available, any positive value will be considered as a positive response.

The number (%) of subjects mounting a response will be summarized and descriptively compared with the proportion from the UCLA “Fresh” study. In addition, the number (%) of subjects with a response to each of the individual criteria will be summarized.

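### In subjects transfused at harvest, the baseline for the 6-month ADA criterion follows the donor red cells; with no baseline, any positive value passes

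*SAP*

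**What the plan says.** - **Criterion.** SAP 8.3.1.1 scores the ADA component as "ADA activity in red blood cells: change from baseline >0 Units". A responder must also meet the CD3 and gene-marking thresholds. The result is reported as number and percentage and compared descriptively with the fresh-product study.
- **Missing baseline.** The same section adds: "if ADA activity at baseline is not available, any positive value will be considered as a positive response".
- **Which sample is baseline.** SAP 8.3.1.1 and 8.3.3.6 do not say. The SAP does define baseline, as the last evaluation before infusion, for quality of life (8.3.2.3), haematology (8.4.6.1), biochemistry (8.4.6.2) and vital signs (8.4.7).
- **Scheduled sample.** SAP Table 1 has one pre-infusion erythrocyte ADA entry, in the Baseline column (Visit 3, Assessment C, Day -10 to -4). Protocol 5.1.3 places these samples after harvest and "if the autologous OTL-101 product has met the release criteria". For younger subjects the time may move: "Measurements of erythrocyte ADA enzymatic activity and erythrocyte deoxyadenine nucleotide levels. These tests can be performed at any time following BM harvest". Footnote 12 of SAP Table 1 gives the limits: "These test can be performed at anytime following BM harvest (Visit 2: Assessment B) and prior to OTL-101 administration".
- **Transfusion.** SAP Table 1 has a row "PRBC transfusion" marked at the harvest visit, which is timed as "Approx 30 day prior to Visit 3F". Protocol 5.1.2 says: "Compatible irradiated PRBC (10 to 15 cc/kg) may be transfused following the completion of marrow harvest", if the investigator thinks it appropriate.

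**The concern.** The criterion asks whether the subject's red cells carry more ADA at Month 6 than before treatment. Donor red cells bring normal ADA with them (Protocol 7.2 refers to a normal-donor reference range for erythrocyte activity). If they are present in the baseline sample and gone by Month 6, a genuine rise can be scored as no rise. No section of either document deals with transfusion when scoring this criterion.

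The missing-baseline rule errs the other way. Protocol 4.1 requires ADA to be decreased, not absent, and Protocol 1.1.1 speaks of residual activity. A positive Month 6 value therefore need not show a treatment effect. The protocol's own rationale (2.1) is that activity above the pre-treatment level at 6 months is predictive, and the fallback drops that comparison.

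ADA is one of three all-or-nothing components of a primary endpoint used to support comparability with the fresh product. For a subject who meets the other two, ADA alone decides responder status.

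**Working it through.** **1. The plan's own figure.** Protocol 9.4 states 15% precision for 100% success with N=10. The exact 95% lower limit for 10/10 is 0.025^(1/10) = 0.6915, and the half-width is (1 - 0.6915)/2 = 0.154. The figure reproduces and is not in dispute. SAP 8.3.1.1 plans no interval for the responder proportion.

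**2. Days from harvest to the baseline draw (t).**
- SAP Table 1, with harvest about 30 days before Day 0 and baseline at Day -10 to -4: 30 - 10 = 20 to 30 - 4 = 26 days.
- Protocol 3.5 and 5.1.3, with 30 to 45 days to manufacture and release and baseline after release: 30 to 45 days or later.
- Footnote 12, younger subjects: t can be close to 0. A draw between the end of harvest and the start of transfusion would be allowed, but nothing asks for it.
- Harvest to the earliest Month 6 visit: 30 + 182.6 - 14 = about 199 days.

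**3. Donor share of red cells at baseline.** The PRBC volume (10 to 15 mL/kg) is from Protocol 5.1.2. The other inputs are assumptions from outside the documents: PRBC haematocrit 0.55 to 0.70, blood volume 75 to 85 mL/kg, pre-transfusion haematocrit 0.30 to 0.36, and linear loss of donor cells over 120 days.

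D = volume x PRBC haematocrit x (1 - t/120); P = blood volume x patient haematocrit; share s = D/(D + P).

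| Timing | Lowest s | Highest s |
|---|---|---|
| t near 0 | 5.50/(5.50 + 30.6) = 15% | 10.5/(10.5 + 22.5) = 32% |
| 20 to 26 days | 4.31/(4.31 + 30.6) = 12% | 8.75/(8.75 + 22.5) = 28% |
| 30 to 45 days | 3.44/(3.44 + 30.6) = 10% | 7.88/(7.88 + 22.5) = 26% |

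At 199 days s = 0, since 199 exceeds 120. Wider assumptions (PRBC haematocrit up to 0.80, blood volume from 70 mL/kg, donor-cell survival 60 to 120 days) give 11% to 32% at day 20 and 5% to 27% at day 41.

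**4. When this produces a false failure.** Let B be the subject's own pre-treatment activity, N the donor activity and A the Month 6 activity, all per unit of red cells, with donor cells keeping full activity. The measured baseline is (1 - s)B + sN. A true rise (A > B) is scored as failure only if A - B is no larger than s(N - B). With s at 12% to 28%, that means a rise no larger than 12% to 28% of the gap between the subject's pre-treatment level and the donor level. The documents give no value for A, B or N, so the share is not an error rate.

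**5. When the missing-baseline rule produces a false pass.** The test becomes A > 0. A subject with B > 0 and A no higher than B passes the ADA component. The documents do not say how often a baseline will be missing.

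**6. Effect on the endpoint.** One subject whose ADA result is wrong and who meets the other two criteria moves the proportion by 1/5 = 20 points at the first analysis, or 1/10 = 10 points with all ten.

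**The case against.** **The baseline is identifiable.** A reader might infer that the plan has no ADA baseline at all. That goes too far: Protocol 5.1.3 is the Baseline visit and lists erythrocyte ADA, and SAP Table 1 has a single entry in its Baseline column. This stands. The problem is that the sample so identified follows any harvest transfusion.

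**Not everyone is transfused.** Protocol 1.4.2.2 and the Table 1 row might suggest that every subject is, but Protocol 5.1.2 makes it discretionary. Untransfused subjects are unaffected.

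**The wordings.** A reader might see three rival definitions. Above baseline (>0 Units), in Protocol 3.2.1 and 9.3.1, and change from baseline >0, in the SAP, mean the same thing. Only the plain RBC ADA >0 form (Protocol 6.2.1.1, 9.1, 9.4; SAP 1) differs.

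**No evidence that misclassification will occur.** Protocol 2.1 reports that ADA in the fresh studies peaks at 3 months and then stabilises. Month 6 values may lie well clear of a raised baseline. Likewise, Protocol 4.1 accepts other cell types or mutations alone, so it does not prove residual erythrocyte activity. Both points stand and limit the claim to a possible bias.

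**A missing baseline looks unlikely.** The sample is mandatory and the window is wide in younger subjects. That is fair, but the rule was written for the case and decides it in one direction.

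**Much will be visible.** Response by criterion (SAP 8.3.1.1), individual ADA plots (8.3.3.6) and transfusion counts (8.2.12) would partly expose a problem. They would not correct the responder count.

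**Withdrawal and the enrolment halt.** One might infer that this flaw will trigger them. SAP 5.1 and Protocol 3.6.1 do tie non-response to both, but the halt refers to the Protocol 3.2.1 criteria and awaits investigation of the cause. How those passages fit together is a separate question.

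**Conclusion.** The point holds as a possible bias in one component of a primary endpoint, in two groups only: subjects transfused at harvest (towards false ADA failure) and subjects with no baseline (towards false ADA pass). The sequence of harvest, discretionary transfusion and baseline sample is clear from the documents. Clearance of donor cells by Month 6 rests on the assumed 120-day survival, and the donor share of roughly 10% to 28% at the standard baseline draw rests on the haematocrit and blood-volume assumptions shown. The number of subjects affected cannot be estimated from the documents. The consequence per affected subject is 20 points at N=5 or 10 points at N=10, provided the CD3 and marking criteria are met. This is an inexpensive improvement worth making; it does not show that the responder result will be wrong.

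**What to change.** 1. **Draw and define the baseline.** Take the baseline erythrocyte ADA sample before any harvest transfusion, at the existing Assessment A draw. State in SAP 8.3.1.1 that the ADA baseline is the last value before that transfusion. For subjects already harvested, use an earlier comparable pre-transfusion erythrocyte value if one exists; otherwise flag the baseline as post-transfusion.
2. **Show both outcomes.** For subjects with a missing or flagged baseline, give the responder count with the ADA component taken as met and again as not met, instead of relying only on the any-positive-value rule.
3. **Report two readings and align the wording.** Give the absolute >0 reading beside change from baseline for the cryopreserved and fresh cohorts, because the fresh study's baseline timing is not in the documents. Align the plain RBC ADA >0 wording in Protocol 9.1 and 9.4 and SAP 1 with the endpoint definition. Protocol 6.2.1.1 uses the plain form in its rule on resuming ERT; the sponsor must reconcile that passage with the endpoint, and no clinical rule is proposed here.

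**Cost.** A small extra blood volume within 5 days before a 15-20 ml/kg marrow harvest, in children whose obtainable blood volumes the protocol calls limited (5.1.7). It also needs edits to the schedules, Protocol 5.1.2 and 5.1.3 and SAP 8.3.1.1, and two readings to report, since a pre-transfusion baseline may not exist in the fresh cohort. If no sample can be added, the definition, the flag and the two-way count need only text changes and a little extra analysis.

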8.3.1.2 Overall Survival at 12 Months

Overall survival will be evaluated using the time in months from transplant to either the subject’s death or their last evaluation calculated as:

$$12 * (\text{date of death/last evaluation} - \text{date of transplant}) / 365.25.$$

The number (%) of subjects who were still alive at 12 months post-transplant will be summarized. For the purpose of this analysis, any subject who withdrew from the study prior to 12 months, who was known to be alive at the last evaluation, will have a status of “unknown”. The proportion and exact 95% confidence interval (CI) for survivors at 12 months post-transplant will be calculated.

Overall survival will also be represented using a Kaplan-Meier curve for time to death. For the purpose of this analysis, any subject who withdrew from the study prior to 12 months and was known to be alive at the last evaluation will be censored at the date of their last evaluation. If appropriate, the proportion alive at 12 months and the associated 95% CI will be estimated from the Kaplan-Meier curve along with the median survival time (and interquartile range), if they can be estimated from the data.

8.3.1.3 Event Free Survival at 12 Months

Event-free survival will be evaluated using the time in months from transplant to either the first event or their last evaluation calculated as:

$$12 * (\text{date of event/last evaluation} - \text{date of transplant}) / 365.25.$$

For the purpose of this analysis, the events of interest are:

- death;
- reinstitution of PEG-ADA ERT;
- requirement for a second transplant.

Event-free survival will be summarized in the same way as overall survival described in Section 8.3.1.2.

8.3.2 Secondary Efficacy Endpoints

8.3.2.1 Overall and Event Free Survival at 24 Months

Overall and event-free survival at 24 months will be summarized in the same way as for the analyses at 12 months described in Sections 8.3.1.2 and 8.3.1.3.

